## Population

Our genotype-first study IMAGINE-1 recruited 3,402 children from UK NHS Regional Genetics Clinics, whose intellectual disability (ID) is associated with either a pathogenic Copy Number Variant (CNV- 75.9%) or Single Nucleotide Variant (SNV- 23.6%) or both (0.5%). 84% of consented families provided standardized assessments of their child's mental health, functional adaptation, medical and educational history, and family/social environment, by completing online questionnaires. We have data on 4,054 genetic variants, logged for 3,398 individuals, representing 3,117 CNVs (1,534 in recognised syndromes, 1,583 unique) and 944 SNVs in 278 different genes. 57% of IMAGINE-1 participants had one or more psychiatric diagnoses: Autism Spectrum Disorders (38%); ADHD (24%); anxiety disorders (12%); challenging behaviour (13%). 31% had a history of seizures, of whom 57% take anticonvulsant medication.

A subset of this group comprised 520 individuals with a specific range of CNVs and their siblings. These comprised children with 16 CNVs across 9 loci. All families in this subset were visited at home for individual face-to-face assessments and agreed to be re-contacted for future studies. We aim to make contact at least 500 participant families. With permission (and with due regard to Covid restrictions) they will be reassessed during a face-to-face visit, with a focus on the affected child as well as the children's unaffected (control) siblings who had been recruited as part of IMAGINE-1.

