The GMM will be carried out using the maximum likelihood with robust standard errors estimator, which is robust to non-normality in the data. Full information maximum likelihood (FIML) will be used to accommodate missing data in problem behaviour and adaptive functioning. Under the assumption that the data are missing at random (MAR), FIML can estimate parameters using any available information that is contained in the dataset. FIML is also considered superior to other techniques used to handle missing data in terms of bias and the sampling variability of the parameter estimates produced. To avoid model convergence to local maxima, we may increase the number of random starts. We will follow a classic three-step analysis whereby, upon selection of the optimal latent class model, the latent class variable is extracted and used as an observed variable for further testing. We note that one-step approaches whereby the latent class variable is extracted and examined in terms of its associations with covariates and outcomes in the same analytical step are frequently used, but they can be problematic when examining a large number of covariates.

In addition, simulations have shown that in models with high entropy values, the covariates do not influence class assignment to a large extent. Upon examination of the distribution of the covariates

across the extracted classes, we will run regression models to measure the associations between class membership and outcomes at the final follow-up assessment (e.g. worsened/improved/no change). We will use linear, logistic, ordered logistic and multinomial regression models, depending on the scale of measurement of each outcome. Potential moderators of risk include: environmental variables (Index of Multiple Deprivation, ethnicity, parental education); biological variables including age, sex, medical history (including treatments for neurodevelopmental disorders); and genotypic variables such as whether the genetic anomaly was inherited or *de novo*, and mutational burden (e.g. sum of the lengths of CNVs containing neurodevelopmental genes).

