From the HES data, the control cohort will be matched to the IMAGINE-2 study group in age range, gender, ethnicity and index of multiple deprivations. Patterns of healthcare usage will be identified and their association with developmental trajectories of mental health will be evaluated, revealing any differences between cohorts. Incidence rates of the hospital episodes will be derived by age (from birth) and analysed using negative binomial or Poisson regression, allowing for a random intercept per child to account for longitudinal nature of the HES data.

We will identify clusters of similar usage and test the extent to which the composition of clusters is influenced by genetic, familial and environmental factors in IMAGINE-2 cohort. They also will be grouped according to how they interact with healthcare facilities and their healthcare use trajectories using group based multi-trajectory model / sequence analysis. Mixed model regression and latent class analysis will be employed to compare domain-specific trajectories between the IMAGINE-2 and control cohorts. Specific patterns of NHS facility usage associated with the trajectories will be determined, accounting for child's age, sex, demographic variables (including age of genetic diagnosis) and health characteristics (genetic condition, medical or surgical interventions, mental health problems). As a result of these analyses, points of strength and weakness in hospital services can be identified in both cohorts.

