### **Workstream 2: Data analytic strategy**

The approach we propose for the longitudinal investigation is based on our findings from the IMAGINE-1 study, as well as our longitudinal studies of children with rare CNV. These have indicated that longitudinal follow-up of children with pathogenic CNVs is feasible and informative and that specific childhood factors predict adverse outcomes in adolescence (risk of psychotic disorder). Our analysis indicates that CNV genotype, when included as a factor in our models, explained only 6-22%

of variance in phenotypic outcome, depending on trait. Thus, the majority of the phenotypic variation is not attributable to the CNV but to other factors. It therefore will be important for better understanding of variability in phenotypic outcomes to study the extent to which other genetic variation and environmental risk factors play a role.

Previous work by our group, including a study in collaboration with the 22q11.2DS IBBC, has indicated that Polygenic Risk Scores (PRS) for schizophrenia (derived from a study of patients with that condition) can be used to predict the risk of schizophrenia as an outcome in people possessing pathogenic CNVs. In addition to extrinsic genetic sources of phenotypic variability, the study of characteristics intrinsic to each CNV will also be informative (i.e., CNV size and gene content). For example, previous studies have provided evidence that the number of constrained genes within a CNV may contribute cumulatively to variability in cognitive outcome. Furthermore, there is evidence that the specific gene content of a CNV may also influence risk. Our findings from IMAGINE-1 indicate that children carrying inherited genetic variants are more likely to have neurodevelopmental, emotional and behavioural disorders than children who carry a *de novo* variant. Inherited mutations were associated with higher multiple social deprivation scores, suggesting that the worse outcomes in this group might be reflect the impact of parental mutation (carrier) on the psychosocial environment of these families. Thus, the study of salient environmental factors affecting risk is also likely to be fruitful.

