iv) The regression models in ii) will be expanded to include a) polygenic risk scores (PRS), which will be generated using the publicly available summary statistics from large GWAS of schizophrenia, ADHD, ASD and IQ. Each PRS will be regressed against each trajectory measure as described above. These regression models will also consider the effects of environmental factors (e.g., inheritance status of CNV, whether *de novo* or inherited), family socio-economic adversity, family and parent-child relationship quality, parental psychopathology, and experiences of bullying). The effects of environmental factors on the trajectory measures will be tested directly in the regression analyses and we will also be able to include a factor representing change over time in an environmental risk factor. For factors with significant effects (after accounting for multiple testing), their influence in modifying the effects of CNV status on trajectory will be tested by including a CNV\*environmental factor interaction term in the regression. Information on second hits and genetic variation intrinsic to the CNV will be examined in individual models for each CNV only. Where appropriate, we will

investigate whether specific factors influence the analysis above, including family socio-economic status and child history of physical health problems and medication use.

v) Key adolescent outcomes, including prodromal risk for psychosis, internalising disorder and persistence of neurodevelopmental disorders, will be extracted via data linkage, as discussed earlier. The effects of trajectory (and CNV status) on these outcomes will be assessed by logistic regression, considering relevant environmental factors.

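### Workstream 1 lists summed CNV length as a moderator and names only ordinary regressions, with no term for the variant that children share; if genotype affects the outcome, a burden test rejects more often than nominal

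*Protocol*

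**What the plan says.** In section 6.1, Workstream 1, trajectory classes are extracted and then related to outcomes at the final follow-up: "We will use linear, logistic, ordered logistic and multinomial regression models, depending on the scale of measurement of each outcome". The same paragraph gives an open list of potential moderators. Its genotypic entries are inheritance status and "mutational burden (e.g. sum of the lengths of CNVs containing neurodevelopmental genes"). It names no random effect, stratum or clustered standard error for the variant.

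Three other places bear on this:

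- **Population section:** the logged variants are described as "representing 3,117 CNVs (1,534 in recognised syndromes, 1,583 unique) and 944 SNVs in 278 different genes".
- **Section 6.1, Workstream 2, data analytic strategy:** "CNV genotype, when included as a factor in our models, explained only 6-22" per cent of phenotypic variance, depending on the trait. The same text names CNV size as a characteristic intrinsic to the CNV.
- **Workstream 2, item iv:** "Information on second hits and genetic variation intrinsic to the CNV will be examined in individual models for each CNV only".

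So Workstream 2 studies this kind of variable within each CNV. Workstream 1 lists it for pooled regressions and has no equivalent restriction.

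**The concern.** Summed CNV length is close to a property of the variant rather than of the child. When a covariate hardly varies within a group and the group also affects the outcome, the information about the covariate comes mainly from the number of groups. A regression that counts children gives a standard error that is too small.

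Workstream 1 aims to find risk and protective factors, biological ones included. Behavioural differences between a few common syndromes that happen to be long or short could then be reported as a general effect of burden, with intervals that are too narrow.

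**Working it through.** The protocol states no alpha, power or error rate for a Workstream 1 burden analysis, and its power paragraph covers Workstream 2 only. There is therefore no figure to reproduce.

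**Inputs from the protocol**

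- Cohort: 3,402 children ("Our genotype-first study IMAGINE-1 recruited 3,402 children from UK NHS Regional Genetics Clinics"), split as "pathogenic Copy Number Variant (CNV- 75.9%) or Single Nucleotide Variant (SNV- 23.6%) or both (0.5"%).
- CNV carriers: (75.9% + 0.5%) × 3,402 ≈ 2,599. SNV only, with CNV length zero: 23.6% × 3,402 ≈ 803.
- Recurrent CNVs: 1,534 / 3,117 = 49%. Taking one per carrier leaves 2,599 − 1,534 = 1,065 carriers with unique CNVs only.
- Variants per child: 4,054 / 3,398 = 1.19, so length is nearly but not exactly constant within a syndrome.
- Genotype share of variance, ρ: 0.06 to 0.22.
- Carriers per CNV: the only figure derivable is from the Workstream 2 power paragraph, 500 / 13 = 38.5.

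**Assumptions**

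- Two-sided 5%.
- ρ carries over to Workstream 1 outcomes.
- 16 to 200 distinct syndromes.
- Log-normal lengths.
- A second CNV in 15-19% of children.

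**Closed form, recurrent carriers only.** For a covariate constant within groups of size m:

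design effect = 1 + ρ(m − 1); true type I error = 2[1 − Φ(1.96 / √design effect)]

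| m | ρ = 0.06 | ρ = 0.22 |
|---|---|---|
| 38.5 (500/13) | 3.25, error 28% | 9.24, error 52% |
| 30.7 (1,534/50) | 2.78, error 24% | 7.53, error 48% |
| 15.3 (1,534/100) | 1.86, error 15% | 4.15, error 34% |

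This leaves out the children with unique CNVs or SNVs only, who dilute the effect.

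**Simulation with those children included.** There is no true burden effect, the outcome is continuous, the full cohort is used, and the model is ordinary regression. Ranges reflect different assumptions within a row.

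| Clustering | ρ = 0.06 | ρ = 0.22 |
|---|---|---|
| 1,534 carriers in 16 genotypes | 24-31% | 49% |
| in 50 | 13-24% | 29-43% |
| in 100 | 9-19% | 20-38% |
| in 200, equal sizes | 8% | 14% |
| floor: only 500 children in 13 CNVs share a variant | 7% | 15% |

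With ρ = 0 the simulation returns 3-6%, as it should. Keeping half the cohort (16 to 100 genotypes) gives 7-22% and 16-41%.

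**Other forms of the test**

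- *Binary outcome, 20% in the class* (floor case and 50 to 200 genotypes): 4-16% at ρ = 0.06 and 10-32% at ρ = 0.22.
- *Class-by-burden interaction with genotype-specific class slopes* (CNV carriers, 50% follow-up, 16 to 200 syndromes): about 6-9% and 9-20%.
- *Interaction when genotype only shifts the outcome level* (16 to 100 syndromes): 4.6-6.4% if class is independent of genotype. If class depends moderately on genotype: 5.6-6.7% at ρ = 0.06 and 6-10% at ρ = 0.22.

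**Remedies.** A random genotype intercept brought the rate to 3.7-5.6% in every setting tried, with ρ taken as known. Estimated by REML in CNV carriers it gave about 5-6%. Uncorrected cluster-robust errors gave 5.4-11.4%. These checks of the random intercept used linear models only.

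**The case against.** The strongest objection is that no burden test is written down. The sentence on regressions relates class membership to outcome. Burden is one illustrative entry in a list of potential moderators, with no model, alpha or decision rule. Read literally, a moderator is an interaction with class, where the inflation is much smaller. Error structure is also commonly left to a statistical analysis plan, which may exist and is not shown.

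This limits what can be claimed. A reader might infer four stronger things that the protocol does not support:

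- *That the protocol declares children independent.* It does not. This follows only from the models named, and naming a regression family does not exclude a random intercept.
- *That 6-22% is the intra-cluster correlation for this analysis.* The figure stands in the Workstream 2 rationale, varies by trait, and has 22% as an upper figure in the power paragraph. It is not an estimate for SDQ-based outcomes.
- *That the hospital-episode analysis already handles comparable structure.* Its model, "allowing for a random intercept per child to account for longitudinal nature of the HES data", deals with repeated records on one child, not with a variant shared between children.
- *That the test rejects far too often in every case.* The 1,583 unique CNVs share no variant, and with many small syndromes or a categorical outcome the rate can be near nominal.

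What remains is this. The protocol's stated aim of finding variables associated with better or worse outcomes allows a main-effect reading. On that reading the direction of the error is clear whenever genotype matters, and Workstream 1 lacks the restriction that Workstream 2 places on the same kind of variable.

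**Conclusion.** The point holds as a conditional one. A burden test from the regressions named is anti-conservative if genotype explains part of the Workstream 1 outcome variance. For a continuous outcome in the full cohort, a nominal 5% test rejects about 7-31% of the time at a genotype share of 6%, and about 14-49% at 22%. For a binary outcome or an interaction with class the inflation is smaller and can vanish at 6%. Where the study falls in these ranges depends on the number and sizes of syndromes, which the protocol does not give, and on carrying over the 6-22%. This is worth correcting before analysis. It does not touch the trajectory model itself, or covariates that vary freely between children with the same variant.

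**What to change.** In section 6.1, Workstream 1, after the list of moderators, add that any regression testing burden, or another covariate fixed mainly by the variant, will include a random intercept for the primary recurrent CNV or syndrome, or for the gene. For a child with several variants, the primary pathogenic one defines the cluster; a unique variant is its own cluster. If burden is tested as an interaction with class, add a random slope for class by variant. This slope follows from the data structure and was not simulated.

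Where a mixed ordinal or multinomial model does not converge, use cluster-robust standard errors by variant with a small-sample correction, since the uncorrected form repaired the level only in part. State also whether burden is meant as a main effect or as a moderator of class.

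The cost is a short addition to the text, a grouping variable derived from variants already logged, and a rule for choosing the primary variant. Mixed categorical models with many single-child clusters will be harder to fit. Intervals for burden will be wider and its apparent power lower.

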	
control cohorts (pseudonymised control data from individuals without intellectual disability, NHS Digital)
 
- Data linkage to National Pupil Database (NPD)
 
- Development and Wellbeing questionnaire
 
- Annual follow-up (for 5 years):
 
 
- Strengths and Difficulties Questionnaire
 
- Everyday Feelings Questionnaire
 
- Adaptive behaviours assessment Schedule
 
- Family Life Questionnaire
 
- Wessex Scales
 
- Demographic updates
 
- Impact of COVID-19 on mental health
 
- Study Impact Questionnaire
 
 
Workstream 2:
 
 
- Modified Lewis scale
 
- Child and Adolescent Psychiatric Assessment (CAPA)
 
- Autism Diagnostic Interview–Revised (ADI-R)
 
- Structured interview for Prodromal Symptoms (SIPS)
 
- Autism Diagnostic Observation Schedule (ADOS)
 
- Wechsler Abbreviated Scales of Intelligence-2nd Edition (WASI-II)
 
- Developmental Behaviour Checklist (DBC)
 
- Wisconsin Card Sorting Test (WCST)
 
- Computerised Neurocognitive Battery (CNB)
 
- Family Environment Scale
 
- Iowa Family Interaction Rating Scales
 
- Life events checklist
 
- Physical Health (including seizures and epilepsy) and medication use
 
- Development Coordination Disorder Questionnaire (DCDQ)
 
- Strengths and Difficulties Questionnaire (SDQ – parent and teacher reports)
 
- Social Communication Questionnaire (SCQ)
 
- Social Responsiveness Scale (SRS)
 
- Repetitive Behavior Scale Revised (RBSR)
 
- Pubertal development (Peterson assessment)
 
- Child Eating Behaviour Questionnaire (CEBQ)
 
- Hyperphagia Questionnaire (HQ)
 
- Epilepsy screening questionnaire (ESQ)
 
- Blood and saliva sample collection
 
- Eating Disorder Examination Adolescent Questionnaire (EDE-A)
 
- Pica, ARFID, and Rumination Disorder Interview (PARDI-AR-Q)
 
- ARFID brief screener (ARFID-BS)
 
- Nine Item ARFID screen (NIAS)
 

--	--

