## IMAGINE-1

### Workstream 1 inclusion criteria:

*Inclusion criteria for 'proband' (e.g. child with rare genetic disorder):*

1. A generalised intellectual disability or developmental delay diagnosis made by a specialist physician
2. Diagnostic microarray analysis of DNA and/or next-generation sequencing
3. At least one CNV or SNV reported as being clinically significant
4. Has a legal guardian available who can consent and can provide detailed medical and behavioural history
5. Aged 4 to 26 years old at recruitment

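### Hospital episode rates are compared with controls by age from birth, but IMAGINE children entered only after specialist diagnosis and genetic testing, so part of any pre-entry difference can reflect ascertainment

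*Protocol*

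**What the plan says.** Four things in the Protocol bear on this point.

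- **Time origin and model** (section 6.1, Workstream 1, hospital records): "Incidence rates of the hospital episodes will be derived by age (from birth) and analysed using negative binomial or Poisson regression", with a random intercept per child.
- **Controls.** The same paragraph states that "the control cohort will be matched to the IMAGINE-2 study group in age range, gender, ethnicity and index of multiple deprivations". The synopsis (section 3) describes the source as "pseudonymised control data from individuals without intellectual disability, NHS Digital".
- **Purpose.** The comparison is explicit: "Patterns of healthcare usage will be identified and their association with developmental trajectories of mental health will be evaluated, revealing any differences between cohorts". The hospital-records text closes by expecting to find where hospital services do well and badly in both cohorts.
- **Entry of the IMAGINE children.** The Population section says the first study "recruited 3,402 children from UK NHS Regional Genetics Clinics". Section 4.4 requires "A generalised intellectual disability or developmental delay diagnosis made by a specialist physician", then "Diagnostic microarray analysis of DNA and/or next-generation sequencing", and "Aged 4 to 26 years old at recruitment".

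The nearest safeguard is that age at genetic diagnosis is listed among the covariates for the usage-pattern analysis.

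**The concern.** A child's early years enter the IMAGINE side of the comparison only because that child later reached a specialist, was tested and was recruited. Contacts on the route to diagnosis therefore lie in counted time, in one cohort only. Children who come often to hospital may also be more likely to be diagnosed and found. Controls have no matching event. Their past is not selected on later contact with specialist or genetic services.

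Two consequences follow. A difference before diagnosis or recruitment can partly reflect ascertainment, and the rate model has no term that separates this from a difference in need or in service provision. In addition, IMAGINE children had to survive to entry, while nothing says that controls must be alive at a corresponding age. At stake is how the early-age contrast is read, especially if it feeds statements about the quality of services.

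**Working it through.** The Protocol states no episode rate, rate ratio or power for this comparison. The power figures in section 6.1 are for Workstream 2. There is no figure to reproduce, so the check has two parts: reading the texts together, and testing direction under assumed rates.

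**Reading the texts together**

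- Entry is possible at ages 4 to 26, and section 4.1 says most children were 6 to 13 when first seen. With recruitment as entry, all IMAGINE time below age 4 is pre-entry. From 4 upward a band mixes both kinds: at age 8, a child recruited at 6 contributes post-entry time and a child recruited at 13 contributes pre-entry time. Deriving rates by age therefore does not separate the periods.
- Matching on age range gives a control no index age.
- A random intercept handles correlation within a child, not selection into the cohort.
- Age at genetic diagnosis is undefined for controls, and it is not a time split in the rate model.

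**A. Work-up contacts counted as episodes (all inputs assumed)**

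Let b be the control rate per year, k the extra episodes on the route to diagnosis, a the entry age, and 15 the end of follow-up. With no true difference:

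- ratio before entry = (b·a + k)/(b·a)
- ratio from birth to 15 = (15b + k)/(15b)
- ratio after entry = 1.00

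| b | k | a | before entry | birth to 15 |
|---|---|---|---|---|
| 0.5 | 1 | 8 | (4+1)/4 = 1.25 | (7.5+1)/7.5 = 1.13 |
| 0.3 | 1 | 8 | (2.4+1)/2.4 = 1.42 | (4.5+1)/4.5 = 1.22 |
| 0.3 | 3 | 8 | (2.4+3)/2.4 = 2.25 | (4.5+3)/4.5 = 1.67 |
| 0.1 | 3 | 4 | (0.4+3)/0.4 = 8.50 | (1.5+3)/1.5 = 3.00 |

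Over b = 0.1, 0.3, 0.5, k = 1 or 3, and a = 4 or 8, the ranges are 1.25 to 8.50 before entry and 1.13 to 3.00 from birth to 15. With k = 0 both ratios are 1.00.

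**B. Entry that depends on earlier contact (simulation, all inputs assumed)**

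Episodes follow a Poisson distribution with a gamma frailty of mean 1 and variance 0.5 or 1.0. The rate is 0.3 per year in both cohorts, entry is at age 8 and follow-up ends at 15. The chance of entry is 1 − (1 − p)^n, where n is the number of episodes before age 8 and p = 0.05, 0.2 or 0.5. With no true difference:

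- before entry: 1.44 to 2.27
- birth to 15: 1.35 to 2.09
- after entry: 1.24 to 1.90

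Children who used hospital more before entry go on using it more afterwards, so post-entry time reduces this selection but does not remove it.

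**C. Survival to age 4 (all inputs assumed)**

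Suppose the true ratio is 2 in survivors, and a fraction d dies before 4, on average at 2, with m times the survivors' episode rate. For all births, the ratio at ages 0 to 4 is 2·[4(1 − d) + 2dm]/[4(1 − d) + 2d].

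- d = 0.02, m = 3: 2 × 4.04/3.96 = 2.04
- d = 0.10, m = 10: 2 × 5.60/3.80 = 2.95

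Counting survivors only gives 2.00. Conditioning on survival lowers the observed excess.

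**The case against.** The strongest reply is that birth is a defensible origin. The variant is carried from birth, so time before recruitment is exposed time. Work-up contacts are real use of hospitals by these children, and recruitment is an administrative date. Making post-recruitment time the main comparison would remove birth to age 4 for every child and most of childhood for many, which changes the question. This stands, and it is why the from-birth description should be kept.

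A second reply is that the plan derives rates by age and states no single lifetime ratio, so work-up contacts would show at the ages at which they occurred. That is correct, and a reader who infers one pooled rate goes beyond the text. What remains is the mixing within age bands.

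A third is that the size depends on the assumption. In illustration A any positive k gives a ratio above 1. The Protocol does not say whether inpatient, outpatient or emergency data are used. If only admissions count, k may be close to 0 and this part of the effect close to nil. This stands too.

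A fourth is that index ages and time splits are details for a statistical analysis plan, which is not at hand. In part, yes. But the time origin, the matching factors and the comparative purpose are fixed in the Protocol, and as fixed they leave the two periods unseparated.

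Finally, the closing statement on services follows several analyses, some of them adjusted, and does not rest on the rate model alone. That limits the consequence. It does not supply an index age for controls.

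**Conclusion.** The point holds as a limited one. The Protocol compares age-specific episode rates from birth between a cohort ascertained through health services and controls with no corresponding entry event. Part of any difference before diagnosis or recruitment can be due to that ascertainment.

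Three stronger readings are not supported.

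- That the entry criteria do create an excess of a known size: the document reports no excess and no rates, and the ranges above are illustrations of direction only.
- That the age-4 condition adds to the excess: it works the other way if children who die early are heavy users and controls are not also required to survive.
- That post-recruitment time is free of the problem: a ratio of 1.00 after entry holds only in the simplest model, and selection through prior contact still gave 1.24 to 1.90.

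The net direction and size are therefore unknown. The change is a worthwhile and cheap improvement, not a correction of an invalid analysis.

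**What to change.** - Keep the description of rates by age from birth.
- Give each matched control the IMAGINE child's index age, at genetic diagnosis or at recruitment, chosen in advance. Require the control to be alive and under follow-up at that age. If diagnosis is chosen, state that the time between diagnosis and recruitment is still conditional on survival.
- Add a before/after-index term by cohort to the same negative binomial or Poisson model, and report the two rate ratios separately.
- State which hospital data sets count as episodes, and add a sensitivity analysis that sets aside genetics and diagnostic work-up episodes.
- Do not rest conclusions about strengths and weaknesses of services on the pre-index contrast alone. State that post-index rates reduce, but do not remove, selection through prior contact.

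The same model and linked records serve. The cost is a little more analysis work, the assignment of index ages to controls, and wider intervals within each period than for the whole of follow-up.
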